4.5 Consent Process

The research coordinator and a representative from the medical team will confirm the patient's eligibility for the study based on inclusion and exclusion criteria. Patients will be given time to ask questions about the study to determine whether they are interested in participating. Our research team will utilize both in-person recruitment and remote/eConsents as applicable. The research coordinator will review the study and its risks with the patient and those interested in participating will sign informed consent and complete a Health Insurance Portability and Accountability Act (HIPAA) form in accordance with institutional guidelines.

For the remote consent option, access to the consent forms will be available digitally or via paper copies of the consent forms sent through the mail. A member of the study team will contact the patient via phone or over a HIPAA-compliant tele/videoconference line to verbally review the consent process with the patient. The patient will be granted time to consider and discuss the study before deciding to participate. If the patient decides to participate, they can either provide their electronic signature in an electronic consent platform, or they can sign a paper copy of the consent form that has been mailed to them. If the patient chooses to sign a paper copy of the consent, the patient will be mailed two copies of the consent form along with a self-addressed stamped envelope (SASE). One copy of the consent form will be to sign and for the patient to keep for themselves, and the second will be signed and mailed back to the study team.

4.5.1 Randomization Procedures

After consent is obtained, participant information will be entered into an electronic study portal to complete enrollment and perform randomization. Participants will be randomized to either the USDA Mediterranean-style Food Pattern or to standardized guidance on fiber intake in a 2:1 allocation ratio, respectively. Randomization failures, defined as a patient who agreed to randomization but whose treatment was allocated in a non-random fashion or was randomized under inaccurate information and occurring within the first week of randomization will be recorded as protocol violations, described in detail in 11.0.

4.5.2 Those who decline randomization

Participants who decline randomization and participation may be asked to complete a short survey assessing their interest in participating in a future trial of medical management.

4.6 USDA Mediterranean-style Food Pattern/ Medi for all

Participants randomized to the USDA Mediterranean-style Food Pattern Arm (called Medi for all) will have access to a "toolbox" that includes education materials (e.g., food pattern tables according to daily caloric intake), recipes, grocery lists, group-based online dietary support, feedback, and reminders to encourage dietary change. Recipes and grocery lists can be individualized to a participant's food budget and preferences. Materials will be available in print and Web-based. This state-of-the art intervention will then use electronic feedback in the form of nudge messages designed to motivate participants to sustain or improve adherence to the Med-style Food Pattern. Every two weeks, participants in the intervention arm will be prompted via a

digital online platform⁹⁶ (analog also available) to complete the 14-item Mediterranean Diet Assessment Score (an adapted version of the MEDAS Score¹⁴⁵ previously used in the PREDIMED34 study) for the purpose of providing timely, individual feedback on diet adherence (not for assessing adherence to the diet pattern). The MEDAS score will be calculated via the online digital platform and ranked according to 3 cutpoints: ≤ 7 , 8–9, or ≥ 10 .¹⁴⁵ Patients will be encouraged to achieve a score of ≥ 10 which is considered high adherence. The platform will then offer feedback based on the levels of self-reported adherence to the diet including self vs. peer comparisons and support resources. Nudge messages will utilize information from a baseline assessment of participants’ dietary attitudes and beliefs about which food groups within a Med-style food pattern they perceive to be most within their control. Ultimately, this approach will enable us to provide participants with dietary information and services that support adherence by accounting for attitudes, norms, and perceived control.¹⁴⁶⁻¹⁴⁸ The extent of interaction with the online platform will be assessed bi-weekly; degree of adherence to the USDA Med-style food pattern; and engagement in dietician services will be assessed at quarterly intervals.

4.7 High Fiber Diet Arm

Participants randomized to the High Fiber Diet Arm will be given commonly used patient education pamphlet,¹⁴⁹ describing fiber and high-fiber foods, the rationale for increasing fiber intake, and ways patients can promote greater intake. Based on prior observational studies of incident diverticulitis, at least 25 grams/day of fiber will be recommended for participants.

5.0 Study Schedule Overview, Research Assessments, Medical Record Review, Call Triggers, Withdrawal, Compensation, and Retention

5.1 Study Schedule Overview

Consented and randomized participants will be asked to complete research assessments on the topics and at the time points described in Table 1. Research coordinators (RCs) or study team members will offer baseline and follow-up assessments in multiple modalities in order of participant preference (e.g., online, on paper, or over the phone). Participants randomized to the USDA Healthy Med Style food pattern (Medi for All) will receive electronic nudges to support behavior change. Additionally, the study dietitian will provide online group counseling sessions and office hours for participants to schedule individual online follow up counseling sessions which will provide additional content related to wellness, self-efficacy and motivation.

Table 1. Participant Assessment Schedule.

| Item | Baseline | Bi-Weekly | Monthly | Follow-Up Time Point | | | |
|-------------------------------|----------|-----------|---------|----------------------|---|---|----|
| | | | | Month | | | |
| | | | | 3 | 6 | 9 | 12 |
| Contact Information | x | | | x | x | x | x |
| Food Frequency Questionnaires | x | | | | x | | x |
| Online Diet Program | x | x | | x | | | x |
| Blood and Stool Sample* | x | | | | x | | x |
| DVQOL | x | | | | x | | x |

| | | | | | | | |
|--|---|---|--|---|---|---|---|
| IPAQ | X | | | | x | | x |
| Gastrointestinal Quality of Life (GIQLI) ²² | x | | | | x | | x |
| Mediterranean Diet Assessment Score (MEDAS) | | x | | x | x | x | x |
| Adverse Events | | | | x | x | x | x |
| Self-Reported Weight | x | | | | x | | x |
| Diverticulitis Symptoms & HCU | x | | | x | x | x | x |
| Beyond Demographics | x | | | | | | |

*Up to 40 participants will be also invited to submit a stool sample for fecal calprotectin analysis. This will be collected at baseline, 6 months, and 12 months.

To ensure successful retention of participants and completion of research assessments through the follow-up period, detailed contact information including name, address, phone numbers, email addresses, as well as alternate contact persons and phone numbers will be requested from participants at baseline (and updated at subsequent time points). While complete contact information is ideal to optimize future retention, only one means of contacting the participant is required for enrollment. For participants with upcoming travel plans abroad or who may live internationally, it is preferred that they provide phone and email contact information as mailed contact is slow and costly for the short windows around each research assessment.

5.2 Research Assessments

5.2.1 Baseline Assessment (Index Encounter)

The Baseline Assessment as listed in Table 1 should be completed in-person or online and *prior to revealing the participant's random treatment assignment*; however, research coordinators are asked to document when the participant became aware of their assignment, should it be revealed prior to completion of the Baseline Assessment.

- Survey questions will be presented in the order of importance in the event that the participant is unable to complete the full battery of questionnaires.
- Collection and Measurement of Inflammatory Markers: We will collect and store blood samples on all participants. For the exploratory aim of this pilot study, we will measure inflammatory markers in plasma drawn in up to 40 participants. Blood samples will be collected in purple top EDTA tubes (EDTA plasma will be collected and stored for future studies) and immediately processed at room temperature.
- Collection of Stool for Measurement of Fecal Calprotectin and Future Studies: Participants may collect stool samples for future microbiome and metabolome analyses using an easy-to-use kit including catchment materials placed under the toilet lid and a small spatula/spoon. For stool collection, the spatula/spoon will be dipped into the fecal material and 1-5 g (peanut sized sample) will be obtained and placed in a clean, screw-top vial. Another small sample will be obtained and placed in another identical vial containing ethanol with instructions to screw lid tightly and shake. To optimize stability of the specimens, the vials should be refrigerated until shipping or transport.

- Participants randomized to Medi For All will participate in an introductory session regarding a USDA Healthy Med-style Food Pattern. Participants will have access to a “toolbox” that includes education materials (e.g., food pattern tables according to daily caloric intake), recipes, grocery lists, group-based online dietary support, feedback, and reminders to encourage dietary change. Recipes and grocery lists can be individualized to a participant’s food budget and preferences. Materials will be available in print and Web-based. This state-of-the-art intervention will then use electronic feedback in the form of nudge messages designed to motivate participants to sustain or improve adherence to the intervention. They will also be offered 6L of extra virgin olive oil (EVOO) over the 12-month study period, free of charge, if interested. Participants randomized to the fiber arm will be offered 6L of EVOO at the end of the 12-month study period, free of charge, if interested.

5.2.2 Bi-Weekly Check-in

Participants in the Medi For All intervention will be prompted every other week via a digital online platform (analog also available) to complete the 14-item Mediterranean Diet Assessment Score (MEDAS Score), slightly adapted for a US population, for the purpose of providing timely, individual feedback on diet adherence. The MEDAS Score will be calculated via the online digital platform and ranked according to 3 cutpoints; ≤ 7 , 8–9, or ≥ 10 . Patients will be encouraged to achieve a score of ≥ 10 which is considered high adherence. The platform will then offer feedback based on the levels of self-reported adherence to the diet including self vs. peer comparisons and support resources (such as group sessions and recipes). Nudge messages will utilize information from a baseline assessment of participants’ dietary attitudes and beliefs about which food groups within a Med-style food pattern they perceive to be most within their control.

The extent of interaction with the online platform will be assessed bi-weekly; degree of adherence to the USDA Med-style food pattern; and engagement in dietician services will be assessed at quarterly intervals. Study staff will utilize a multi-modal (email, phone call, text, etc.) outreach for participants who fail to complete the MEDAS Score when prompted.

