5.3 Medical Record Review

Time points

Participants will have their EMR reviewed at ad-hoc time points if triggered by a survey response or if they have a diverticulitis event. Study staff will conduct an EMR review to assess the following:

1. Complications for patients using the National Surgical Quality Improvement Program (NSQIP) definitions and protocol; and
2. The following information related to diverticular disease:
 - a. Indication for healthcare utilization
 - b. Length of stay (if hospitalized);
 - c. Surgery type, if applicable.

As needed, chart review will be conducted if a patient reports an adverse event and further documentation is needed.

Data Collection

Data will be collected using the following forms:

| Form | Description |
|-------------|--------------------|
|-------------|--------------------|

| | |
|-----------------------------|--|
| Form Information | Captures information about when the form was filled out (time point), and by whom |
| Enrollment Form | Completed at index visit only; captures basic demographics and treatment assignment data; medical history and cohort designation |
| Healthcare Utilization Form | Captures information about any visit (date, setting, treatments, medications) |
| Adverse Events Form | Captures information about adverse events at any time point |

If a participant seeks care at an outside hospital, the study team will work with the participant to obtain relevant information.

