8.5 Secondary Statistical Analyses

Binary and categorical endpoints (e.g., adverse events and complications) will be tabulated by intervention group. Time in healthcare will be summarized by group using medians and interquartile ranges, and differences between intervention groups will be summarized using 95% confidence intervals generated from generalized linear regression models appropriate for each type of outcome (e.g., binary, count, continuous, etc.). To examine the sensitivity of adherence to the Med-style Food Pattern on changes in serum biomarkers, we will modify the primary analytic model described for Aim 2 by separately adjusting for a binary indicator of adherence (adherent vs. not) and a graded measure of adherence to intervention. Finally, we will use

mediation analyses to explore the extent to which changes in serum biomarkers over time are mediated through intervention-induced changes in weight and physical activity.

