8.7 Sample Size and Statistical Power

Using 2:1 randomization, we will enroll 50 patients into a USDA Med-style Food Pattern and 25 patients to receive standardized guidance on fiber intake. The analytic aim of this study is to inform potential effect sizes and variance estimates toward the ultimate goal of conducting a definitive phase 3 randomized trial. While 1:1 randomization is more statistically efficient when group variances in outcome are similar, we plan to enroll more participants into the USDA Med-style food pattern intervention to strengthen the precision of estimates of adherence and patient-reported response. Since statistical testing will not be formally conducted, statistical power was not a primary motivation for sizing for this pilot study.¹⁶⁶ However, enrollment of 50 study participants in the USDA Med-style Food Pattern intervention allows a 95% one-sided confidence interval for the intervention adherence rate to exclude rates less than 0.70 if the observed adherence rate is 0.80 or higher in this pilot study.

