9.0 Study Related SAEs

9.1 Identification of SAEs

Randomized participants will be monitored for SAEs throughout their study surveillance period (enrollment through twelve months). The occurrence of an SAE may come to the attention of study personnel during study follow-up phone interview or by a study participant calling the study team or presenting for medical care. Study staff will use the EMR to fill out the SAE form. The PI will then complete the form and sign the form. The SAE form will then be submitted to the DCC who will provide it to the ISM. The ISM will review the SAE form and ask the study team for additional clarification or specification as he/she sees necessary.

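### Extra staff contact in the Med-style arm alone can tilt the by-arm table of adverse events and complications, because events reported at any time are counted and the route is not recorded

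*Combined protocol and SAP*

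**What the plan says.** **Contact.** Section 5.2.2 states: "Participants in the Medi For All intervention will be prompted every other week via a digital online platform". The prompt is a 14-item diet score, given "for the purpose of providing timely, individual feedback on diet adherence". A missed prompt leads to personal follow-up: "Study staff will utilize a multi-modal (email, phone call, text, etc.) outreach for participants who fail to complete the MEDAS Score when prompted". Section 5.1, directly after describing the Med-style nudges, says that "the study dietitian will provide online group counseling sessions and office hours for participants to schedule individual online follow up counseling sessions". Section 5.2.1 adds an introductory session for that arm. Section 4.7 describes a pamphlet and a fiber target for the other arm and no contact between assessments.

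**Event collection.** Table 1 schedules adverse events, and diverticulitis symptoms with healthcare use, at months 3, 6, 9 and 12 for all randomized participants. Table 2 makes diverticulitis events a self-reported quarterly outcome and also sets NSQIP complications quarterly. Outside that schedule, section 5.2.3 has staff pass on any AE or complication reported to them, and the Adverse Events Form in section 5.3 "Captures information about adverse events at any time point". For serious AEs, section 9.1 says: "The occurrence of an SAE may come to the attention of study personnel during study follow-up phone interview or by a study participant calling". A care visit is the third route named there. Record review under section 5.3 is ad hoc: it follows a survey response, a diverticulitis event or, as needed, a reported AE.

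**Analysis.** Section 8.5: "Binary and categorical endpoints (e.g., adverse events and complications) will be tabulated by intervention group". It has no rule on route of detection, and no listed form is described as recording it.

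**The concern.** A participant who misses a diet prompt because of illness or an admission is one whom staff then try to reach by telephone, text or email. Whatever that person mentions can go onto the AE form and can open the medical record. Section 6.2 says complications are recorded as AEs through record review, so opening a chart can itself add events. An equally ill fiber-arm participant gets no such contact between quarterly assessments, and no fixed chart review would make up for it.

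At stake is how the by-arm safety table is read. Extra detection would add events on the Med-style side, which could look like harm or hide a benefit. Section 8.7 gives the analytic aim as informing potential effect sizes for a phase 3 trial, and Aim 1 says that trial will focus on recurrence and complications. If the same forms and contact pattern carry forward, the distortion does not shrink as the sample grows, whereas the sampling error that hides it here does. Without a record of route, it may not be possible to reconstruct the problem afterward.

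**Working it through.** The plan gives no figure for event detection, so there is none to reproduce. Its one sizing figure (section 8.7) concerns adherence and does not enter here.

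**Step 1: count the contacts.** Every two weeks for 12 months is 52/2 = 26 prompts, Med-style arm only. Quarterly assessments are 4 in each arm. That makes 26 + 4 = 30 scheduled contacts against 4, before dietitian sessions and outreach. Occasions on which event questions are scheduled are 4 against 4, because the prompt is a diet score with no event item described.

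**Step 2: trace how an event reaches the table.**

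| Route | Med-style | Fiber |
|---|---|---|
| Quarterly AE and diverticulitis questions | yes | yes |
| Participant calls the team or presents for care | yes | yes |
| Mentioned during outreach after a missed prompt | yes | not described |
| Mentioned in a dietitian session | yes | not described |
| Chart review after a report | after any of the above | after the first two only |

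The last three rows are where the arms differ. The plan neither assigns event collection to outreach or dietitian staff nor prevents them from passing on what they hear.

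**Step 3: illustrate the size.** Arm sizes are from section 8.7: "we will enroll 50 patients into a USDA Med-style Food Pattern and 25 patients to receive standardized guidance on fiber intake". Let r be the true 12-month risk, equal in both arms, and dM and dF the probabilities that an event is recorded. Then:

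- expected recorded events = 50 × r × dM and 25 × r × dF
- apparent risk ratio = dM/dF
- apparent risk difference = r × (dM − dF)
- 95% half-width = 1.96 × √[a(1−a)/50 + b(1−b)/25], with a = r × dM and b = r × dF

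Neither r nor the detection probabilities are in the documents, so all are assumptions. Section 2.0 mentions recurrence in at least 20% after a first episode, with no time frame. I use r = 20% for scale and 10% to 30% as the range. At r = 20%:

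| dM, dF | Recorded events | Risk ratio | Risk difference (points) | 95% half-width (points) |
|---|---|---|---|---|
| 0.90, 0.90 | 9.0/50 vs 4.5/25 | 1.00 | 0.0 | 18.4 |
| 0.95, 0.90 | 9.5/50 vs 4.5/25 | 1.06 | +1.0 | 18.6 |
| 0.90, 0.80 | 9.0/50 vs 4.0/25 | 1.125 | +2.0 | 17.9 |
| 0.90, 0.70 | 9.0/50 vs 3.5/25 | 1.29 | +4.0 | 17.3 |

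For the third row: a = 0.18, b = 0.16, and 1.96 × √(0.002952 + 0.005376) = 0.179.

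Over r = 10% to 30%, the third row's difference runs from +1.0 to +3.0 points and the fourth row's from +2.0 to +6.0. Half-widths across all rows run from about 13 to 21 points. Against equal detection at 0.90, the last two rows lose 0.5 and 1.0 of the 4.5 expected fiber-arm events.

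**The case against.** The strongest reply is that event questions are asked on the same schedule in both arms. An extra contact then mostly brings forward something the next quarterly assessment would have found. This largely holds for diverticulitis events: Table 2 already defines them as quarterly self-report, and section 5.2.7 keeps diverticulitis symptoms among the priority questions even in a shortened assessment. It holds less well for AEs. Section 5.2.7 does not name AE questions as a priority and prefers missed answers to withdrawal. Where a quarterly assessment is missed or shortened, the fiber arm loses its only scheduled AE questioning, while a Med-style participant may still be in contact.

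It is also fair to say that the routes section 9.1 names for serious AEs are open to both arms, that section 5.2.3 invites every participant to contact the coordinator, and that individual dietitian sessions are optional. A reader might infer from 30 contacts against 4 that detection differs in that proportion, or that section 9.1 admits events from any contact. The documents support neither. Leakage comes through the wider intake in sections 5.2.3 and 5.3.

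Finally, these are secondary or safety outcomes, described without formal tests, and the primary outcomes are feasibility measures. Section 8.4 ties effect-size estimation to biomarkers and patient-reported outcomes, and section 8.7 does not name AEs. All of this stands and limits the consequence in the pilot. It does not remove the asymmetry from the table.

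**Conclusion.** The by-arm tabulation of AEs and complications can be tilted toward more events in the Med-style arm. This rests on four features of the plan: one-sided contact between assessments, recording of AEs reported at any time, chart review that is triggered rather than fixed, and a table that ignores route. It also assumes that staff who hear of an event pass it on, as section 5.2.3 asks. Section 8.1 says data-collection staff are blinded, and the plan does not say whether they are the staff who chase missed prompts.

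The size is unknown. Under assumed detection gaps of 5 to 20 points the apparent risk ratio is 1.06 to 1.29, and at 20% risk the shift of 1 to 4 points sits well inside a half-width of 17 to 19 points. A reader might go further and conclude that the counts will be inflated, or that the diverticulitis comparison is equally affected. The documents do not support either. No event question is attached to the extra contacts, and the diverticulitis outcome has a common quarterly basis, with residual exposure only through triggered record review, ad hoc reports and any difference in retention.

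**What to change.** 1. On the Adverse Events and Healthcare Utilization forms, record the route and date of first knowledge, and whether the event was also reported at the next quarterly assessment. The second item is needed because first route alone would drop Med-style events that outreach merely found early, which would tilt the table the other way.
2. In section 8.5, keep the by-arm table of all events, with deaths and serious AEs counted whatever the route.
3. Add a by-arm table limited to events reported at the common quarterly assessments, including those first learned earlier by another route. Use it for the between-arm comparison of non-serious AEs and self-reported diverticulitis events, and show quarterly completion by arm beside it, since the restriction does not correct for differential completion.
4. Leave section 9 safety handling unchanged.

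The cost is a few fields on two forms, a short addition to section 8.5 and one extra table. The comparative table will count somewhat fewer events than the full one.
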